6.1.7. Derived Variables

6.1.7.1. General

- Age: Age will be calculated as the integer difference in years between the subject's year of informed consent and the year of birth.
- Change from baseline: The value at the target time point minus the value at baseline.
- Prior and concomitant medications: All medications taken prior to Screening or in the time interval between Screening and Enrollment/Visit 1 will be considered prior medications, whether or not they were stopped before Enrollment/Visit 1. Any medications continuing or starting after Enrollment/Baseline Visit will be considered concomitant. If a medication starts before enrollment and continues after enrollment it will be considered both prior and concomitant.
- **Study Day:** For analysis purposes, Study Day is calculated relative to the date of first dose of study drug. For study days on or after treatment start, study date = date treatment start date + 1. For study days before treatment start, study day = date treatment start date.
- Treatment-emergent adverse event (TEAE): Defined as 1) AEs with onset at the time of or following the start of treatment with IP through Week 8 (EOT) or 2) AEs starting prior to the start of treatment but increasing in severity or relationship at the time of, or following, the start of treatment with IP through Week 8 (EOT).

[figure not shown]

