6.1.8. Data Adjustments/Handling/Conventions

All collected data will be presented in listings. Data not subject to analysis according to this plan will not appear in any tables or graphs but will be included only in the data listings.

All p values will be displayed in four decimals and rounded using standard scientific notation (eg, 0.XXXX). If a p value less than 0.0001 occurs, it will be shown in tables as < 0.0001.

Adverse events will be coded using the MedDRA version 27.1 thesaurus.

A treatment related AE is any AE with a relationship to the study drug of possibly related.

If partial start dates occur for AEs, prior medications, or concomitant medications, the convention for replacing missing dates for the purpose of statistical analysis is as follows:

- If the year is missing do not impute
- If only the day is missing and the month and year match the first dose date and the end date is on or after the first dose date, then the day assigned is equal to the first dose date; if the month and/or year do not match the first dose date or the end date is prior to the first dose date, then the day is assigned 01.
- If only the month is missing and the day and year match the first dose date and the end date is on or after the first dose date, then the month assigned is equal to the first dose date; if the day and/or year do match the first dose date or the end date is prior to the first dose date, then the month assigned is JAN.
- If both the month and day are missing and the year matches the first dose date and the end date is on or after the first dose date, then the date assigned is the first dose date; if the year does not match the first dose date or the end is prior to the first dose date, then the day/month is assigned 01JAN.

Partial end dates will not be imputed.

7. Study Patients/Subjects and Demographics

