9.1. Adverse Events

Missing and partially missing start dates will be imputed for the purpose of analysis as described in Section 6.1.8.

All adverse events (AEs), treatment emergent adverse events (TEAEs), and serious adverse events (SAEs) will be coded using the MedDRA v. 27.1. Treatment Emergent AEs are defined in Section 6.1.7.1.

The number and percent of subjects reporting treatment emergent AEs, grouped by MedDRA SOC and PT, will be tabulated. In the case of multiple occurrences of the same TEAE within the same subject, each subject will only be counted once for each PT.

A summary table will be created summarizing the number and percent of subjects with the following:

- At least one TEAE
- At least one possibly related TEAE
- At least one serious TEAE
- At least one serious TEAE possibly related to Study Drug
- At least one TEAE leading to permanent treatment discontinuation
- At least one TEAE leading to Death
- At least one TEAE by maximum severity

In addition, the following TEAE data will be summarized for each MedDRA SOC and PT:

- Incidence of overall TEAEs by SOC and PT
- Incidence of TEAEs by SOC, PT, and Severity
- Incidence of Severe TEAE by SOC and PT
- Incidence of TEAEs by SOC, PT, and Relationship
- Incidence of Related TEAEs by SOC and PT
- Incidence of Serious TEAEs by SOC and PT
- Incidence of TEAEs leading to Study Discontinuation

In the summaries showing severity and relationship to study medication the event with the maximum severity (Life Threatening>Severe>Moderate>Mild) or relationship (Related/Not Related) will be reported. If a particular event is missing the severity and/or relationship, then the strongest possible severity or relationship will be assumed for analysis (severity = severe, relationship = related).

In the AE data listings, all AEs will be displayed. AEs that are not treatment-emergent will be flagged. A listing of all AE data sorted by subject, including verbatim term, MedDRA SOC and PT, and all other information from the AE eCRF will be generated.

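### SAP 6.1.8: the rule for AE start dates with only the month missing contradicts itself, and on either reading it usually dates same-year on-treatment AEs before first dose

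*SAP*

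**What the plan says.** SAP 6.1.8 gives one set of rules for partial start dates of AEs and of prior and concomitant medications. Three bullets matter here.

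- **Day missing.** The fallback applies "if the month and/or year do not match the first dose date".
- **Month missing.** The first-dose month is used under a condition whose last part compares the end date with first dose: "If only the month is missing and the day and year match the first dose date and the end date is on or after". January is the fallback, printed as "if the day and/or year do match the first dose date or the end date is prior to the first dose date, then the month".
- **Month and day missing.** The first dose date is used under this condition: "If both the month and day are missing and the year matches the first dose date", again with an end date on or after first dose.

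Partial end dates are not imputed.

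SAP 9.1 carries these dates into the safety analysis: "Missing and partially missing start dates will be imputed for the purpose of analysis as described in Section 6.1.8". Under SAP 6.1.7.1 a TEAE is one of "AEs with onset at the time of or following the start of treatment with IP through Week 8 (EOT"), or an earlier AE that increases in severity or relationship on treatment. Protocol 10.4.5 limits AE analysis to TEAEs. Other AEs appear in the listings, flagged as not treatment-emergent (SAP 9.1).

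**The concern.** There are two faults in one bullet.

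First, the fallback lacks the 'not' found in the parallel bullets. As printed, a record matching first dose on both day and year satisfies both branches. A record matching on neither, with an end date not before first dose, satisfies none. A programmer has to guess.

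Second, restoring the 'not' does not cure it. A same-year AE whose day of month differs from the first-dose day still goes to January. The day of month says nothing about whether an AE began before or after treatment started. An AE for which only the year is known takes the first dose date and counts as a TEAE, while the same AE with its day also known can be sent to January and lost. More information gives the less cautious answer. That runs against the rest of SAP 9.1, which assumes the strongest severity and relationship when either is missing.

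At stake are the TEAE incidence, related, serious and discontinuation tables.

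**Working it through.** The plan states no figure for this, so there is none to reproduce. The rule was coded and applied to every possible case.

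**Inputs from the documents**
- Branch conditions: SAP 6.1.8, as above.
- TEAE definition: SAP 6.1.7.1.
- Treatment period 56 days: Protocol Table 2.
- Screening at most 42 days: Protocol 8.1.2. AEs collected from consent: Protocol 8.4.1.
- 47 participants enrolled: SAP 3.2.

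**Assumptions.** First dose is equally likely on any day of a calendar year. True onset is equally likely on Days 1–56. Day and year are known, the month is missing, and a complete end date falls on or after onset. The documents give neither dosing dates nor a count of such records.

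**Readings.** A is the printed text. B restores the 'not'.

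**Result for first doses in 2022 or 2023.** Pairs: 365 × 56 = 20,440, of which 18,900 have onset in the first-dose year.

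| | Reading A | Reading B |
|---|---|---|
| Dated before first dose | 17,371 (85.0%) | 17,371 (85.0%) |
| Meets both branches | 692 (3.4%) | – |
| Meets no branch | 1,509 (7.4%) | – |
| Dated on or after first dose | 868 (4.2%) | 3,069 (15.0%) |

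- Among same-year onsets: 17,371 / 18,900 = 91.9%.
- Imputed before Day −42: 15,110 / 17,371 = 87.0%.
- For 2024 the corresponding figures are 84.9%, 91.8% and 87.2%.

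**By first-dose month (reading B).** February to October about 96%; November 79%; January 47–48%; December 27%.

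**Worked cases**
1. First dose 15 Jun 2023, true onset 10 Jul 2023 (Day 26). Imputed to 10 Jan 2023 on both readings, so not a TEAE by onset. With the day also missing it would be dated 15 Jun and counted.
2. First dose 15 Jun 2023, true onset 15 Jul 2023. Reading A meets both branches; reading B gives 15 Jun.
3. First dose 20 Dec 2023, true onset 3 Feb 2024. Reading A has no branch; reading B gives 3 Jan 2024, still a TEAE.
4. First dose 5 Jan 2024, true onset 15 Mar 2024 (Day 71, past Week 8 even with its 7-day window). Imputed to 15 Jan on both readings, so a post-EOT AE is counted as a TEAE.

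**Size per participant.** 1 / 47 = 2.1 percentage points.

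**The case against.** The best case against acting is that this may never matter. A start date with day and year but no month is an unusual pattern. Protocol 9.3 asks for AE start dates and for follow-up at each visit, and SAP 4 requires data review before the final analysis. With 47 participants and eight weeks of treatment the expected number of such records may be zero. No AE vanishes from the listings, and one that worsens on treatment can still qualify as a TEAE. All of this stands. It limits the likely effect but does not make the bullet usable.

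Three stronger readings are tempting and are not supported.

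- *The bias can only lower the TEAE count.* Case 4 shows a post-EOT AE being added. Under reading B, a screening AE starting 15 May, with first dose 15 Jun and end date 20 Jun of the same year, is dated 15 Jun and also wrongly counted.
- *Any AE with a known day and year is lost.* The year and end-date conditions matter. A later-year AE goes to January of that later year, after first dose, or has no branch as printed. January and December first doses keep many events in the tables.
- *Simply deleting the bullet and using the year-only rule would do.* That discards a day that can prove pre-treatment onset. With first dose 20 Dec and start day 15, month unknown, of the same year, every possible date precedes dosing, yet the year-only rule assigns 20 Dec if the end date is on or after that date. Applied to medications, it could also move long-standing drugs out of the prior-medication table.

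**Conclusion.** The point holds in a limited form. The month-missing bullet cannot be programmed as printed, and inserting the missing 'not' leaves the main fault in place. For on-treatment AEs with only the month missing and an end date on or after first dose, about 85% are dated before first dose (92% of same-year onsets). About 87% of those dates are earlier than the earliest possible consent.

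The percentages rest on uniform first-dose and onset dates and are conditional on the missing-date pattern occurring. They do not estimate how much the reported TEAE rates would change. That change may be nil, and is about 2.1 points for each participant whose inclusion in a table depends on the misdated event. The predominant direction for on-treatment AEs is loss of TEAEs, but errors in the other direction exist. The correction is still worth making because it is cheap and decides how events are classified.

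**What to change.** Replace the month-missing bullet in SAP 6.1.8, for AEs only, with:

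> *If only the month is missing and the year equals the year of first dose, assign the earliest month that puts the start date on or after the first dose date and not after a known end date. If no such month exists, the AE started before first dose: assign the latest month that puts the start date before first dose and not after a known end date, and treat it as pre-treatment. If the year differs from the year of first dose, assign JAN of the known year.*

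Under this rule all 20,440 enumerated on-treatment onsets are dated on or after first dose. The 20 December example stays pre-treatment.

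For prior and concomitant medications, keep a separate bullet with the 'not' restored, so that long-standing medications stay in the prior-medication table.

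The cost is a few lines of SAP text and separate programming branches for AEs and medications, with no new data. The downside is that some screening AEs continuing past Day 1, and some post-EOT AEs, would be counted as TEAEs when the month is missing. That is the cautious direction the year-only bullet already takes.

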7.1. Disposition of Patients/Subjects and Withdrawals

[figure not shown]
Disposition will include tabulations of the number of subjects who signed an ICF, the number of subjects who received treatment, tabulated reasons for discontinuation from the study, and number of subjects in each of the following analysis populations: ITT, SAF, and PP.

7.2. Protocol Violations and Deviations

Protocol deviations will be tracked, recorded, and reviewed prior to database lock, following the Protocol Deviation Guidance Plan for this study. The deviation list will be stored in Remarque and transferred to the biostatistics team for analysis.

Protocol deviations will be classified as "Important" or "Non-Important." An important deviation poses a possible safety issue to the participant, or it has a potential impact on the statistical analysis of the clinical data. A non-important deviation is identified as any protocol deviation that does not meet the criteria for an important deviation. Recurrent non-important deviations may escalate to the level of important. See PDGP for details.

The final decision regarding classification of deviations and inclusion and exclusion of subjects from the analysis populations will be based on a final listing of protocol deviations. Subject inclusion/exclusion in analysis populations will be determined during a blinded review meeting before study data are unblinded. Clinical and Biostatistics team members will provide input to the decision and the final composition of the analysis populations will be approved by the Sponsor.

Protocol deviations will be summarized for the ITT population. Data will also be presented in a by-subject listing.

7.3. Demographics and Other Baseline Characteristics

For the continuous variables, the number of non-missing values and the mean, standard deviation, minimum, median and maximum will be tabulated.

For the categorical variables, the counts and proportions of each value will be tabulated.

Summary statistics for demographic and other baseline characteristics will be presented overall. Demographic variables will include age, sex, race, ethnicity, height, weight, and body mass index (BMI). Baseline variables will include IGA, %BSA affected, and vital signs. Demographic and baseline characteristic data will be summarized for the ITT and PP populations.

Prior and concomitant medications will be classified by ATC Class Level 2 and preferred term (PT). The number and percentage of subjects taking each classification of medication will be summarized overall. The analysis will be conducted for the ITT population. Data will also be presented in a by-subject listing.

Medical history will be classified by system organ class (SOC) and PT. The number and percentage of subjects with each classification will be summarized overall. The analysis will be conducted for the ITT population. Data will also be presented in a by-subject listing.

8. Efficacy Analysis

8.1. Primary Efficacy Analysis

The primary endpoint will be tested for the following hypothesis:

[figure not shown]
- H₀: There is no difference in the mean TST between Baseline and Week 8 (from the Ōura Ring wearble device).
- H₁: There is a difference in the mean TST between Baseline and Week 8 from the Ōura Ring wearable device).

The average total sleep will be summarized by visit using descriptive statistics. A two-sample paired t-test will be used to test a difference between the average sleep at baseline and Week 8. The mean pair-wise difference, 95% confidence interval of the difference, and p value will be presented. The primary analysis will be conducted on the PP population who also have both a baseline and Week 8 assessment available.

8.1.1. Sensitivity Analysis of the Primary Efficacy Endpoint

A sensitivity analysis will be performed on the primary efficacy endpoint to include those subjects with missing Week 8 sleep results. The sensitivity analysis on the difference in mean TST will be considered for the ITT population.

Missing average TST at Week 8 will be imputed utilizing a Last Observation Carried Forward (LOCF) approach. Because the Ōura Ring data is collected daily, needing at least 4 observations within 7 days to calculate a 7-day average, the last rolling 7-day average that can be calculated

within a subject's TST will be utilized as the observation to carry forward to Week 8.

Similarly to the primary analysis, the average sleep will be summarized at Baseline and the imputed Week 8 using descriptive statistics. The mean pair-wise difference, 95% confidence interval of the difference, and p value will be presented.

8.2. Secondary Efficacy Analysis

The secondary endpoint will be tested for the following hypothesis:

H₀: There is no difference in the mean PROMIS 8b total score between Baseline and Week 8.

[figure not shown]
H₁: There is a difference in the mean TPROMIS 8b total score between Baseline and Week 8.

The average total score will be summarized by visit using descriptive statistics. A two-sample paired t-test will be used to test a difference between the average score at baseline and Week 8 in the ITT population. The mean pair-wise difference, 95% confidence interval of the difference, and *p* value will be presented.

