Following completion of the pretreatment sleep assessment, participants will continue into an 8-week treatment period. On Day 1 of the treatment period, all eligible participants will be enrolled in the study and will begin treating their AD with ruxolitinib cream at the FDA-approved strength (1.5%) BID, applied topically as a thin film. All original areas of AD involvement identified on Day 1 (baseline), regardless of whether or not the lesion(s) improve, and any new and/or expanded areas of AD lesions will be treated until the morning of the Week 8 visit, with a total maximum allowed treatment area of ≤ 20% BSA. Sleep data from each participant will be continuously collected during the treatment period (Day 1 through Day 56 inclusive [or the day before the Week 8 visit]) with both sleep monitoring devices. Measurements of sleep at Week 8 will be compared to baseline in a pair-wise manner to determine the reduction in sleep disturbance. At the end of the treatment period (Week 8/EOT or ET), participants will discontinue treatment with ruxolitinib 1.5% cream (with the last application on the morning of this visit) and will be required to return the eDiary, Ōura Ring, and

Following completion of the treatment period (or the last application of study drug for those who discontinue early), participants will have follow-up assessments 30 (+ 7) days after the end of treatment to evaluate safety.

Throughout the study, at the times indicated in the SoA (see Table 3), participants will complete the following PROs using their eDiary: Itch NRS (daily), PROMIS Sleep Disturbance – Short Form 8b (daily), and PROMIS Sleep-Related Impairment – Short Form 8a (weekly). Additionally, the STOP portion of the STOP-BANG questionnaire will be completed during the screening visit as part of the eligibility assessment. Participants will be assessed for the safety

and tolerability of ruxolitinib cream throughout the study by monitoring the type, frequency, and severity of AEs, performing physical examinations, measuring vital signs, and conducting clinical laboratory assessments, as outlined in the SoA.

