# **6.4.** Study Treatment Compliance

Compliance with all study-related treatments should be emphasized to the participant by the site personnel, and appropriate steps should be taken to optimize compliance during the study. Compliance with study drug will be calculated by the sponsor based on participant responses in the eDiary about study drug application.

Participants will be instructed to bring all empty, partially used, and unused tubes of study drug with them to the study visits in order for site personnel to confirm usage of the study drug.

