## 8.1.4. Visit Reminders and Distribution of eDiary and Sleep Monitoring Devices

Participants will be provided with a reminder notification indicating the date/time of the next visit.

At screening, participants will be issued a handheld device (eDiary) to complete PROs (see Section 8.3) and to record application of study drug. Each participant will be provided

instructions for completing the diary from screening through Week 8 or treatment discontinuation. Compliance with the eDiary will be assessed electronically at the visits noted in the SoA (see Table 3). If the participant is not completing the eDiary frequently enough, the site staff will be informed so compliance can be addressed in a timely manner.

Study sites will contact participants 1 week before the baseline visit to confirm compliance with eDiary assessments. Detailed directions for the administration of the eDiary will be provided in the Study Manual.

During screening, participants will also be provided with a wearable device (Ōura Ring) and a (see Section 8.2.1). It may take up to 7 days during the screening period for the devices to be installed and/or configured and ready for sleep monitoring.

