#### 10.4.3. Secondary Analysis

The secondary endpoint is the PROMIS Sleep Disturbance – Short Form 8b score. A paired t-test will be used to test the hypothesis below for participants with PROMIS Sleep Disturbance – Short Form 8b score at both baseline and Week 8.

 $H_0$ : PROMIS Sleep Disturbance – Short Form 8b score (Week 8) – PROMIS Sleep Disturbance – Short Form 8b score (Baseline) = 0

H1: PROMIS Sleep Disturbance – Short Form 8b score (Week~8) – PROMIS Sleep Disturbance – Short Form 8b score  $(Baseline) \neq 0$ 

Mean, standard deviation, and 95% confidence interval of overall sleep score at each evaluable timepoint will be presented. Mean pair-wise difference and 95% confidence interval of the difference will be presented. The hypotheses above will be tested at level of significance 0.05. The secondary analysis will include participants with both baseline and Week 8 PROMIS Sleep Disturbance – Short Form 8b scores available. Missing data imputation (LOCF) may be considered as a sensitivity analysis.

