9.5. Physical Exams

Whether physical exams were performed at visits will be listed.

10. Changes from Planned Analysis

- Inclusion of the ITT population
- Sponsor decision to cap enrollment at 47 subjects due to enrollment challenges.
- Exclusion of the Sufficiently Treated Population (STP) due to ePRO use challenges
- No formal statistical testing of the exploratory endpoints.

Statistical Analysis Plan, Sponsor: Incyte Corporation Protocol Number: INCB 18424-902 PCN Number: INCY 216559

11. **Other Planned Analysis**

No additional are prospectively planned for this study.

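### The only secondary endpoint (PROMIS 8b) is tested under an ITT label but needs both scores, and no missing-data sensitivity analysis is visible for it

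*SAP*

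**What the plan says.** Protocol 10.4.3 names the endpoint: "The secondary endpoint is the PROMIS Sleep Disturbance – Short Form 8b score". It restricts the paired t-test to participants with both a baseline and a Week 8 score, and adds: "Missing data imputation (LOCF) may be considered as a sensitivity analysis". Protocol 10.4.2 makes the same offer for the primary endpoint, total sleep time (TST).

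SAP Section 5 defines ITT as everyone enrolled, and SAP 3.2 gives that number as 47. SAP 8.2 then uses a paired t-test "to test a difference between the average score at baseline and Week 8 in the ITT population", with no statement that both scores are required. For the primary endpoint, SAP 8.1 does state that requirement, and SAP 8.1.1 takes up the LOCF option: "A sensitivity analysis will be performed on the primary efficacy endpoint to include those subjects with missing Week 8 sleep results". The efficacy table list in SAP 13.2 has two TST tables (14.2.1 in PP, 14.2.1.1 as the ITT sensitivity analysis) and one 8b table (14.2.2, labelled ITT).

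On data capture, Protocol 8.1.4 says "participants will be issued a handheld device (eDiary) to complete PROs (see Section 8.3) and to record application of study drug", and Protocol 4.1 lists 8b as a daily eDiary form. Protocol 6.4 says "Compliance with study drug will be calculated by the sponsor based on participant responses in the eDiary about study drug application". SAP Section 10 lists among the changes: "Exclusion of the Sufficiently Treated Population (STP) due to ePRO use challenges".

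**The concern.** A paired t-test without imputation uses only participants who have both values. Someone reading Table 14.2.2 under an ITT heading would take the mean change to describe all enrolled participants, when it describes those who still had diary data at the end.

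This matters because missing Week 8 scores can depend on outcome. Diary entries stop when treatment stops, and worsening dermatitis is one of the protocol's grounds for stopping. In a single-arm study no comparator shares that loss, so any selection goes straight into the reported change. The plan examines this risk for TST, which comes from the ring, but not for 8b, which comes from the diary.

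**Working it through.** **Is there a figure to reproduce?** No. The documents give no sample size, power or SD for 8b. The only loss allowance is the one for TST in Protocol 10.1: 70 evaluable of 100 enrolled, so 1 − 70/100 = 30%.

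**Who enters the test.** The statistic is the mean of the within-person differences (Week 8 minus baseline). A participant lacking either value has no difference and drops out. This agrees with Protocol 10.4.3. SAP 8.1 states the restriction for TST; SAP 8.2 does not for 8b.

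**Can missingness depend on outcome?** Four places, read together:
- Protocol 8.1.4: diary completion runs to Week 8 or to treatment discontinuation.
- Protocol Table 3: the daily 8b entries end at the last application. (The row label pairs 8b with the name of the other PROMIS form; Protocol 4.1 confirms that 8b is the daily one.)
- Protocol 6.5.2 and 7.1.1: worsening dermatitis that needs a prohibited medication, or treatment over more than 20% BSA, leads to discontinuation.
- SAP 6.1.5: an early termination visit on Days 2 to 55 is assigned to Week 4, and the Week 8 window is Days 56 to 63.

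So a participant who worsens and stops well before Week 8 has no diary scores in the final week, and nothing visible in the SAP supplies one.

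**How large could the effect be?** The documents do not give the share without a pair or the change in those participants, so both are assumed. Let N = 47, n = the number with pairs, f = n/N, C = mean improvement in those with pairs and M = mean improvement in those without. Then:

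all-enrolled mean = f × C + (1 − f) × M

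excess of the completer mean = (1 − f) × (C − M)

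Take C = 6 points as a convenient scale. Protocol 2.2.1 cites 6 points as the threshold for an individual responder, not as an expected mean.

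| Assumed share without a pair | Pairs n | f | All-enrolled mean, M = 0 | All-enrolled mean, M = 3 |
|---|---|---|---|---|
| 0% | 47 | 1.000 | 6.0 | 6.0 |
| 10% | 42 | 0.894 | 5.4 | 5.7 |
| 20% | 38 | 0.809 | 4.9 | 5.4 |
| 30% | 33 | 0.702 | 4.2 | 5.1 |
| 40% | 28 | 0.596 | 3.6 | 4.8 |
| 50% | 24 | 0.511 | 3.1 | 4.5 |

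Worked row at 30%: 47 × 0.70 = 32.9, so 33 pairs; 33/47 = 0.702; 0.702 × 6 = 4.2 if the others are unchanged. If they improve half as much, 0.702 × 6 + 0.298 × 3 = 5.1.

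**The case against.** The strongest reply is that part of the evidence is out of sight. SAP 6.1.4 sends the reader to 6.1.7 for missing PROMIS scores, and SAP 6.1.1 sends the 8b baseline average there too. In the available text 6.1.7 has a subsection for 8a but none for 8b. A scoring, minimum-days or missing-item rule for 8b may therefore exist in removed text, and it would be wrong to say that the SAP has no rule. This stands. Such a rule would not be a sensitivity analysis, however, and none is listed in SAP 8.2, the contents list or the efficacy tables.

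A reader might infer from the dropped STP that much 8b data were lost. The documents do not show that. The SAP says only that there were ePRO use challenges and gives no amount. The link to 8b is an inference from the shared device. The STP threshold was also demanding: 23 of 28 applications in 14 days is 82%, whereas the TST rule needs 4 of 7 nights, 57%. Diary gaps that make the STP unworkable could leave most weekly 8b means intact.

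A reader might also infer an undeclared departure from the protocol. LOCF was optional, and Protocol 10.4 leaves missing-data procedures to the SAP, so its absence from SAP Section 10 is not a breach.

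The labelling point is partly met. SAP 4.1 already requires the number of non-missing values in every continuous summary, and naming ITT as the source set for a paired test is common shorthand.

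Finally, the direction is not certain for every kind of loss. Participants who simply stop using the diary may have done better or worse than the rest. The argument for overstatement is clearest for those who stop treatment because they worsen.

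**Conclusion.** The point holds as an inconsistency that should be corrected. The one secondary endpoint is analysed in participants with both scores under a label that means all 47, and it lacks the missing-data check that the primary endpoint has. Loss of Week 8 scores can be tied to worsening disease, so the completer mean may overstate improvement.

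The size is unknown. The 4.2 against 6 points is an illustration that assumes 30% without a pair and no change in them. The 30% is borrowed from the TST allowance, which also covers device malfunction. The figures do not support a claim that the bias reaches any given share of a clinically meaningful change: the inputs are assumed, and 6 points is a threshold for individuals rather than group means. This concerns a secondary endpoint with no stated power, so it does not affect the primary conclusion.

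**What to change.** 1. In SAP 8.2 and the title of Table 14.2.2, describe the set as ITT participants with both baseline and Week 8 assessments, matching the restriction in SAP 8.1. Report the number of pairs out of 47.
2. Add a repeated-measures model on weekly mean 8b scores for all ITT participants with any 8b data, with baseline as one of the occasions, reporting the Week 8 change. Keep it small. Baseline plus Weeks 1 to 8 is nine occasions, and an unstructured covariance would need 9 × 10/2 = 45 parameters for at most 47 participants. Use AR(1) or compound symmetry, or only baseline, Week 4 and Week 8 (3 × 4/2 = 6 parameters if unstructured).
3. State that this model assumes data are missing at random, so it does not by itself deal with loss that depends on unobserved scores. Beside it, report a no-change analysis that carries the baseline score to Week 8 where Week 8 is missing. Count separately anyone without a baseline score.

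The cost is SAP wording and one or two extra tables on data already collected. The reported improvement may be smaller. If the SAP is already final, identify the additions in the study report as unplanned, which SAP Section 1 allows.
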